### **A. Who will obtain informed consent, and their qualifications:**

All informed consent activities for all participant types and research phases will be obtained by our trained CIDRZ study assessors. The assessors will be highly trained in human subjects and responsible conduct of research and will have the appropriate certifications (e.g., NIH).

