### **B. How, where, and when the consent discussion(s) will occur:**

Consent for participants in Stage 1A will be done in a private room within the HIV clinic or office building where the participant works.

Informed consent from PLWH in Stage 1B will be obtained within a private room within the HIV clinic. This will be done after the patient has been referred to our on-site study assessor by one of their care providers following the recruitment process. Consent will first be obtained for screening. If the participant is eligible following screening, the assessor will then obtain informed consent for the remaining study activities. The second informed consent will be specific to either the cohort or trial study, whichever the participant screened eligible for.

For all consent activities with all participant types, the following information about the study will be discussed:

- Purpose;
- Locations where research will be conducted;
- Points of assessment and the types of questions that will be asked;
- Random assignment to treatments;
- Description of each treatment;
- How privacy will be protected;
- Incentives for research visits and schedule;
- Potential risks;
- Potential benefits;
- The circumstances in which mandated reporting will be required; and
- The participant's rights.

The consent forms will be available in English and two common Zambian languages and consent will occur in the language (among the 3) chosen by the participant. If the participant is not literate in one of the 3 languages, an independent witness (either family member, friend, or clinic staff not working on the study) who is literate in the chosen language will be present and will co-sign the consent. Study procedures will allow for potential participants to take time to make a decision about whether or not to participate and a follow-up appointment within 48 hours of the initial meeting can be scheduled, if desired. The participants will be encouraged to ask questions throughout the consent process and also throughout their entire participation in the study.

C. The process you will use to determine whether a potential participant meets eligibility criteria:

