*Analysis of implementation data.* Mixed methods analysis based on NIH best practice guidelines will be used to integrate findings from the quantitative and qualitative data. Descriptive analyses will be used to investigate the quantitative data on constructs of acceptability, appropriateness, reach, feasibility, and cost. The qualitative data will provide in depth understanding of factors related to (1) mechanisms of change; and (2) barriers and facilitators to program implementation in the Zambian context. Findings will be shared with local (HIV clinics, Lusaka district, and Zambia MoH) and international stakeholders (PEPFAR/CDC, UNAIDS, etc.) to inform future programming efforts.

5. **Answer the following if they are relevant to your study design:**

1. If the study has different arms, explain the process for assigning participants (intervention/control, case/control), including the sequence and timing of the assignment.

The assessor will have two locked cabinets at the clinic with sealed envelopes. One cabinet will contain randomization assignments for female participants, the other for male participants. Printed on the outside of the sealed envelopes will be a Randomization ID. When a participant is eligible for the pilot RCT, the assessor will retrieve the next available envelope and record the Randomization ID and Screening ID on a Screening Information Sheet, thus linking the two IDs to the participant. Randomization IDs will be assigned to BI+CETA or BI alone using *randomize* in Stata *a priori* by a U.S.-based statistician not affiliated with the study. Randomization IDs will be randomized 1:1 in blocks of 20 stratified by sex. The assessor will inform the participant of their assignment by opening the envelope

immediately after the baseline assessment. This ensures that the assessor is blinded to the participant's randomization status during the assessment itself. Follow-up assessments will be conducted by a different assessor.

2. If human biospecimens (blood, urine, saliva, etc.) will be collected, provide details about who will collect the specimen, the volume (ml) and frequency of collection, how the specimen will be used, stored, identified, and disposed of when the study is over. If specimens will be collected for use in future research (beyond this study), complete the "Biospecimen Repository" section below.

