1. Will the study staff be blind to participant intervention status?

Assessors will be blind to participant intervention status. Due to the nature of the interventions, counselors will not be blinded. Data Analysts will also be blinded.

2. Will participants receive standard care or have current therapy stopped?

Participants are already receiving standard of HIV care in Zambia and this will be continued during and after the study. Participants will not be asked to stop any current therapy.

3. Will you use a placebo or non-treatment group, and is that justifiable?

We will not have a non-treatment group. The control group will receive the BI, which is the current standard of care at HIV clinics in Zambia.

4. Explain when you may remove a participant from the study.

Participants will be temporarily removed from the study if they demonstrate actively suicidal or homicidal thoughts. Anyone who develops psychosis in need of hospitalization will also be removed. In any of these events, research assistants, counselors, and supervisors will work together to get appropriate psychiatric assistance for the individual. The study PI and our clinical supervisory team will consult with psychiatric providers in Zambia to determine whether the participants may return to the study following appropriate treatment.

Participants will be removed from the study at their request if they express to us that they do not feel safe.

5. What happens to participants on study intervention when the study ends?

Study interventions will be completed before the end of the study. Following the end of the study, participants who request additional services will be referred to appropriate care.

6. Describe the process for referring participants to care outside the study, if needed.

Some participants may experience emotional distress as a result of participation. Many therapeutic interventions deal with small degrees of stress within a session as part of the treatment. Based on research and experience, the expected degree of distress will be minimal and expected as part of the therapeutic process. In cases where distress does occur during treatment, the participant would be with a trained counselor who will be trained at handling such situations. In addition, these

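### One stated block size of 20 per sex list, with envelopes opened by the role that takes RCT consent: up to about 1 in 11 assignments could be deduced beforehand

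*Combined protocol and SAP*

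**What the plan says.** Section V, item 5.1 sets out the allocation. The sequence is prepared in advance "by a U.S.-based statistician not affiliated with the study", and "Randomization IDs will be randomized 1:1 in blocks of 20 stratified by sex". On custody: "The assessor will have two locked cabinets at the clinic with sealed envelopes", one cabinet for women and one for men. For each eligible person "the assessor will retrieve the next available envelope and record the Randomization ID and Screening ID". Then: "The assessor will inform the participant of their assignment by opening the envelope", straight after the baseline assessment.

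Consent belongs to the same role. Section V.B, part A: "All informed consent activities for all participant types and research phases will be obtained by our trained CIDRZ study assessors". Part B, on the trial- or cohort-specific consent: "If the participant is eligible following screening, the assessor will then obtain informed consent for the remaining study activities".

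Item 6.1 confirms that the treatment is open to those who deliver it: "Due to the nature of the interventions, counselors will not be blinded".

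The plan does not say whether block sizes vary, whether the size is withheld from assessors, whether each clinic has its own lists, or how many assessors share a cabinet. In item 5.1 the trigger for retrieving an envelope is RCT eligibility. That signed RCT consent comes first is implied by the consent section but not stated there.

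**The concern.** In a permuted block of 20, once 10 people have gone to one arm, every remaining place in the block must go to the other. Someone who knows the block size and has seen the earlier openings can tell when that point is reached. Before it, guessing the arm that is behind already does better than chance.

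Here the role that sees the openings also holds the next RCT consent conversation. If that person can foresee the arm, a particular patient can be encouraged or discouraged, even without intent. The arms could then differ before treatment starts. An intent-to-treat analysis does not undo that, because the selection happens before randomisation. The comparison exposed is the primary one, change in AUDIT score, which is meant to support a decision on a later-stage trial.

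**Working it through.** **Inputs**
- Block of 20 at 1:1, so m = 10 per arm; sex is the only stratum (item 5.1).
- 160 randomised (section III.B).
- Two clinics (sections IV and V.A).
- Hazardous drinking expected in 20% of female and 40% of male patients (section III.B).

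**The plan's own figure.** An effect size of 0.5, alpha 0.05 (two-sided assumed) and 80% power give 63.8, so 64 per arm by the t-test, or 128 in total. 128/(1 − 0.20) = 160, as stated. 160/20 = 8 blocks if all are complete. The documents give no figure for predictability.

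**Certain assignments in a completed block.** Position k is certain if one arm was used up in the first k − 1 places:
- position 20: always;
- position 19: 2·C(10,8)/C(20,18) = 90/190 = 47%;
- position 18: 2·C(10,7)/C(20,17) = 240/1140 = 21%;
- position 17: 2·C(10,6)/C(20,16) = 420/4845 = 9%.

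Over all positions the sum is 2m/(m + 1) = 20/11 = 1.82 per block, a share of 1/(m + 1) = 1/11 = 9.1%. Eight complete blocks give 8 × 1.82 = 14.5 of 160.

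**Best guess.** Always naming the arm that is behind is right in [m + 2^(2m−1)/C(2m,m) − 0.5]/(2m) = [10 + 524288/184756 − 0.5]/20 = 61.7% of cases, against 50% by chance.

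**Unfinished blocks.** Certainty falls at the end of a block, so unfinished blocks lower the share.
- Two sex lists: 8.0% to 9.1% for any split with at least 20 per sex. If equal numbers of men and women were screened (an assumption), the expected rates of 40% and 20% give about 107 men and 53 women. That is 5 + 2 = 7 complete blocks, 7 × 1.82 = 12.7 of 160, or 8.0%.
- Separate lists per clinic, same sex split, clinics of equal size (an assumption): lists of about 53, 54, 26 and 27 hold 2 + 2 + 1 + 1 = 6 complete blocks, 6 × 1.82 = 10.9 of 160, or 6.8%. With 50 to 75% male and 50 to 60% of patients at one clinic (assumptions), simulation gives about 7%, with a range of roughly 6 to 8%.
- One list shared across both clinics, assessor sees only one clinic: about 0.01% by simulation.

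**Effect of varied sizes.** Simulation used 80 per list, sizes drawn at random from 12, 16, 20 and 24, and an observer who knows that set but not the order. Certain assignments fall from 9.1% to 0.6%. Best-guess accuracy hardly moves, from 61.7% to 61.5–61.6%.

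**Shorter fixed blocks are not a remedy.** The share 1/(m + 1) rises to 1/3 for blocks of 4, 1/5 for blocks of 8 and 1/6 for blocks of 10.

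**The case against.** The plan has real safeguards. The sequence comes from an outside statistician, envelopes are sealed, a block of 20 is long, and ACASI decides score-based eligibility and the split between RCT and cohort. A different assessor does the follow-up. Referring providers act before AUDIT screening and cannot know whether a patient will reach an envelope, since only about half of hazardous drinkers are expected to qualify for the RCT. All of this stands. It narrows the route for selection mainly to the consent conversation. It does not remove the concern, because the block size is printed in the plan and that conversation stays with the role that opens the envelopes.

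The analysis models change from baseline and allows covariates that differ at baseline. That partly addresses imbalance in measured factors, but not in unmeasured ones.

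Four stronger readings are tempting and go beyond the documents:
- That 1 in 11 assignments actually is known. This needs an assessor who knows the block size, sees every opening in the list and keeps count. The plan neither establishes nor excludes this; the only record it describes at retrieval links the two ID numbers.
- That one individual does both tasks. The documents show the same role, not the same person.
- That staff can use the follow-up appointment within 48 hours to time enrolment. Section V.B offers it to participants who want time to decide.
- That envelopes are opened before RCT consent. The order is left implicit in item 5.1; nothing says that it is reversed.

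**Conclusion.** The weakness is real but bounded. One block size is stated, its concealment is not, and the role that opens envelopes also takes RCT consent. The number of assignments that could be deduced in advance is at most about 1 in 11, some 11 to 14.5 of 160 under the list arrangements worked through above. If lists are shared and each assessor sees only one clinic, it is close to none. The documents do not settle which arrangement applies.

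These figures assume an assessor who knows the size and has a full view of the list. They describe opportunity, not conduct. A reader might infer that the AUDIT comparison will be biased. The documents give no basis for that, or for putting a size on it. The change is worth making because it costs almost nothing before enrolment and cannot be made afterwards.

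**What to change.** In item 5.1:
1. The independent statistician uses randomly varied block sizes of similar length (for example 12, 16, 20 and 24) within each sex list. The sizes are withheld from clinic staff and kept out of the documents they hold.
2. State that the envelope is retrieved only after RCT consent is signed and the baseline assessment is complete.

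The cost is one re-run of the Stata randomisation and a short wording change. If a list stops mid-block, the largest possible imbalance from that block rises from 10 to 12. The gain is in removing near-certain knowledge; a good guesser does about as well as before.

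Optionally, someone other than the consenting assessor opens the envelope. That would return the assessor's guess to 50%, provided results do not leak back. It is sound only if that person does not refer or recruit for the RCT and opens the envelope after the brief intervention has been delivered. Clinic counselors and nurses may both refer patients and deliver the brief intervention that both arms receive. Handing them the unopened envelope beforehand would move the running count to possible recruiters and reveal the arm before they deliver the comparator.

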### Interventions

- World Health Organization mhGAP BI. All participants (regardless of whether RCT criteria are met) will receive a BI. We will provide training to lay counselors (e.g., counselors/nurses already working in the HIV clinics) based on World Health Organization (WHO) mhGAP-Intervention Guide (mhGAP-IG). The mhGAP-IG was developed to provide non-specialists in LMIC with knowledge and skills to deliver low-intensity interventions with fidelity in primary care to treat mental, neurological, and substance use problems. WHO has developed modules to train health care workers. The JHU clinical team in Zambia will adapt these modules to provide a 2-day workshop for counselors at our two clinics. Training will cover components such as: (1) psychoeducation (e.g., examples of ways that hazardous use can be reduced); (2) engagement (e.g., discussing motivations for drinking); (3) personalized feedback and advice (e.g., helping the participant reflect on how use is impacting their life); and (4) encouragement for the participant to change their pattern of use.

Following the baseline assessment, the assessor will notify the on-duty counselor who has been trained in the BI. The BI, which is expected to take 10-15 minutes, will be offered to participants the same day and provided in a private room.

- [Common Elements Treatment Approach \(CETA\)](#). Lay counselors (e.g., HIV peer educators, counselors in the HIV clinics) will be trained to deliver CETA to participants randomized to BI+CETA (i.e., n=80). After enrollment, participants receiving CETA will flexibly meet with their counselor weekly for approximately one-hour sessions, for 6-12 weeks depending on presentation and symptom level. Core elements of CETA sessions are described in Table 2 and will be adapted as needed in Stage 1A.

**Table 2.** Common Elements Treatment Approach

Component	Content	Target
Engagement	Discuss how program helps Identify obstacles to engagement	Promote client buy-in
Safety	Assess client risk for harm to self/others Domestic violence/abuse assessment Initiate safety plan as needed	Assess and address client safety
Empirically-supported cognitive-behavioral elements		
Psychoeducation/Introduction	Program information, normalize symptoms, goal setting	Psychoeducation Reduce stigma

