[Tracking of treatment uptake and completion.](#) We have developed rigorous and sophisticated participant tracking systems through our previous Zambia studies. We will systematically track throughout the course of the study: (1) the number of participants who successfully complete and decline BI; (2) the number of participants who successfully link to CETA, defined as attending the first CETA session; (3) the amount of time counselors dedicate to client tracking/retention; and (4) the number of clients who successfully complete CETA. Counselors will attempt to track clients to the extent that this would be practical in a real-world setting.

[Clinical monitoring data collection.](#) During CETA sessions, the counselor will administer a brief clinical symptom checklist (Client Monitoring Form; CMF) and a past 7-day Alcohol TLFB. These data guide clinical care by informing the choice of CETA elements to be delivered in session and will also be used in analyses. These forms will only be administered to CETA participants during their CETA sessions. (Neither RCT participants randomized to the BI alone nor Cohort study participants will complete the TLFB).

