Data management. All uptake/completion, clinical monitoring, HIV outcome, and uEtG data will be double entered into password protected databases by research staff weekly. ACASI data will be electronically transferred from field laptops at the HIV clinics into the study database at CIDRZ headquarters daily. De-identified data will be transferred to JHU weekly. [name] will run data checks and return queries for resolution. [name] and [name] will hold weekly calls with the Zambian data team.

- Describe the number and type of study visits and/or contacts between the study team and the participant, how long they will last, and where/how they will take place.

Stage 1A: We expect to have two study visits with focus group participants (PLWH and healthcare workers). The first visit will be the recruitment/consent visit. The second visit will be the actual focus group session. The first visit we expect to take approximately 30 minutes. We expect the focus groups to be between 60-90 minutes. We expect to have one study visit for key informants in which we will conduct both the consent and interview. We expect these sessions to be approximately 60-90 minutes. A third contact may be conducted with some of the healthcare workers and key informants at the end of the study to discuss implementation factors in an in-depth interview or focus group. This third visit will be approximately 60-90 minutes in length.

Stage 1B: Participants in the pilot will have an initial study visit for consent/screening/baseline/BI. The initial visit, which includes informed consent and baseline ACASI to capture data, may take up to 120 minutes. If they are randomized to CETA they will have an additional 6-12 weekly therapy sessions (approximately 60 minutes each). All participants will have a post-assessment visit approximately again 6 months post-baseline (we will attempt to have the 6 month assessment align with a regular HIV care visit). The follow-up study assessments we expect to take approximately 45 minutes. We will also ask a sample of participants to participate in a mixed methods interview following the study on implementation outcomes.

- Describe the expected duration of the study from the perspective of the individual participant and duration overall.

From the perspective of participants, the study will be approximately 6 months. Overall, we expect the study to take 3 years, including final data analysis. An estimated timeline is provided below.

**Table 4.** Study timeline

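### As written, the plan appears to reveal allocation before the brief intervention that both arms share; opening the envelope after that session would keep arm knowledge out of it at little cost

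*Combined protocol and SAP*

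**What the plan says.** All references are to the combined protocol and SAP.

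- **Section V, item 5.1 (how participants are assigned).** The form asks here for the sequence and timing of assignment. The answer is "The assessor will inform the participant of their assignment by opening the envelope", and the timing given is "immediately after the baseline assessment. This ensures that the assessor is blinded to the participant's randomization status during the assessment itself". The Randomization ID is linked to the participant when the assessor takes the next sealed envelope.
- **Section V, Interventions, mhGAP BI.** "All participants (regardless of whether RCT criteria are met) will receive a BI". On timing: "Following the baseline assessment, the assessor will notify the on-duty counselor who has been trained in the BI", and "The BI, which is expected to take 10-15 minutes, will be offered to participants the same day".
- **Section V, item 6.1 (blinding).** "Due to the nature of the interventions, counselors will not be blinded". Assessors and data analysts are to be blinded.
- **Section V, number and type of visits.** "Participants in the pilot will have an initial study visit for consent/screening/baseline/BI". Randomization is not placed in this list.
- **Section V, Tracking of treatment uptake and completion.** The items tracked include "the number of participants who successfully complete and decline BI", so the BI can be refused.
- **Section III.B.** The primary endpoint is the between-arm difference in AUDIT change over 6 months. The target is d of at least 0.5, with 64 per arm evaluable and 80 per arm randomized.

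**The concern.** The comparison isolates CETA only if the BI underneath it is the same in both arms. If the arm is known before the BI, several things could differ:

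- A counselor might put more into the session for someone who will get nothing further, or less for someone going on to CETA.
- A participant assigned to CETA might decline the BI as unnecessary.
- A participant told they will get the BI alone might disengage. The consent discussion (Section V.B) covers random assignment and describes each treatment, so that participant knows what the other arm receives.

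Any net difference of this kind becomes part of the AUDIT contrast. Refusal would be visible by arm because it is tracked. Unequal effort or reception would not be, because the plan does not describe recording the length, content or quality of the BI session.

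**Working it through.** **1. Sequence of events.** Item 5.1 puts the opening of the envelope immediately after the baseline assessment. The Interventions section has the assessor call the BI counselor after the same assessment, with the BI to follow that day. If the first step is immediate, the BI comes second. Nothing in the plan supports the reverse order, but no sentence states this order outright, and the visit list does not place randomization.

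**2. What the counselor knows.** Item 6.1 leaves counselors unblinded. No section says that the on-duty BI counselor is told the arm before the session, and none prevents it. The reason given for not blinding, the nature of the interventions, fits CETA but not a session common to both arms.

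**3. Whether the early opening is needed.** The only stated purpose is to keep the assessor blind during the baseline assessment. Opening the envelope after the BI serves that purpose equally well.

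**4. The plan's own sample size.** Inputs from Section III.B: d = 0.5, alpha 0.05, power 80%, 20% dropout. Sidedness is not stated.
- Normal approximation: n = 2(1.96 + 0.84)² / 0.5² = 62.7, so 63 per arm.
- t-test: 63.77, so 64 per arm and 128 in total, as stated. A one-sided test would give 50 per arm, so the plan is two-sided.
- Dropout: 128 / (1 − 0.20) = 160, as stated.
- Power at 64 per arm by t-test: 80.1%.

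**5. Sensitivity to an assumed net shift.** The shifts below are assumptions; the documents give no value. With n = 64 per arm and a two-sided t-test on 126 degrees of freedom, the noncentrality is the standardized difference × √(n/2), and √32 = 5.66. A shift of 0.10 against CETA gives (0.5 − 0.1) × 5.66 = 2.26. The same shift in its favor gives (0.5 + 0.1) × 5.66 = 3.39. With no true effect it gives 0.1 × 5.66 = 0.57.

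| Assumed net shift (SD) | Power at d=0.5, shift against CETA | Power at d=0.5, shift in favor | Two-sided rejection, no true effect |
|---|---|---|---|
| 0 | 80% | 80% | 5% |
| 0.05 | 71% | 87% | 5.9% |
| 0.10 | 61% | 92% | 8.7% |
| 0.20 | 39% | 98% | 20.2% |

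A shift of 0.1 SD is 0.1/0.5 = 20% of the target effect. If the shift runs against CETA, most of the extra rejections in the last column would favor BI alone.

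**6. Cost of the later opening.** The planned N does not change. If a proportion L of eligible participants left before the BI was completed or declined, and so were not randomized, the number of eligible participants needed is 160/(1 − L). The number of hazardous drinkers is twice that before rounding, because Section III.B expects 50% to qualify. L is also an assumption.

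| L | Eligible participants needed | Hazardous drinkers needed |
|---|---|---|
| 0 | 160 | 320 |
| 2% | 164 | 327 |
| 5% | 169 | 337 |
| 10% | 178 | 356 |

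**The case against.** **The order and the counselor's knowledge are inferred.** A reader might conclude that the plan has an unblinded counselor give the BI. The documents do not say that. Item 6.1 is a general statement, and BI and CETA training are described separately. This stands. What the text supports is that the participant appears to know the arm and the counselor is free to know it.

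**The size may be small.** Section II reports that studies of single-session BIs in Uganda and South Africa found no significantly greater reduction than control, and that BIs were not designed for this higher-risk population. The session lasts 10-15 minutes and follows a common two-day training. This stands as a reason to expect the low end of any range. It does not show the shift to be zero, since a participant's reaction to the assignment need not depend on how well the BI works.

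**The direction is not toward a false claim for CETA.** A reader might infer that the design inflates false positives. Three of the mechanisms named above (more effort for BI alone, less effort before CETA, refusal by CETA participants) would dilute the CETA effect; only disengagement in the BI-alone arm would inflate it. The documents do not support a one-directional reading.

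**Knowing what comes next may be part of the strategy.** In real stepped care, patient and counselor may both know whether further treatment follows. That is a legitimate alternative target of estimation. The plan does not claim it, however, and describes the BI as something everyone receives. If the sponsor wants that target, the plan should say so.

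**Reordering does not cure the lack of blinding.** A reader might infer that it removes the bias from knowing the arm. It does not. Participants know their arm through six months of follow-up and report AUDIT themselves. ACASI and a different follow-up assessor do not change that.

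**Conclusion.** The point holds in limited form. As written, allocation appears to be disclosed to the participant, and may be known to the counselor, before a session meant to be common to both arms. The stated reason for the timing does not require this. Any resulting difference in BI effort, reception or refusal would enter the primary contrast, and only refusal is tracked.

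Size and direction are unknown, and the effect of CETA could be diluted or inflated. The figures for a 0.1 SD shift (power of about 61% or 92% instead of 80%, and rejection of 8.7% instead of 5% with no true effect) show sensitivity. They do not estimate a bias. They assume 64 evaluable per arm, a two-sided t-test and a net shift that nothing in the documents supplies.

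This is a worthwhile, inexpensive improvement to the procedures. It does not make the trial invalid. Confidence in the order is moderate to high, because it is the natural reading but not an explicit statement.

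**What to change.** 1. In Section V (Interventions, the visit description and item 5.1), state one order: baseline ACASI; BI completed or declined; envelope retrieved and opened, with the Randomization ID linked to the participant only at that point.
2. In item 6.1, state that the counselor giving the BI is not told the allocation before the session.
3. Add a rule for early leavers. Refusing the BI does not prevent randomization. Anyone who leaves before the BI is completed or declined is not randomized and is reported as a pre-randomization exit. This keeps the intent-to-treat population and the BI uptake denominator clear.

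**Cost.** There are short text changes in four places. The participant returns briefly to the assessor after the 10-15 minute BI, and a few eligible participants may leave before randomization. The visit, staff, sealed envelopes, allocation lists and target of 160 stay the same. If the sponsor already intends this order, the plan only needs to say so.
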